## 1. Summary

**Title:** Safety and feasibility study of Magnetic Seed markers to localise breast cancers for surgical excision

**Short title:** Magnetic seeds to localise breast cancers

**Trial medication:** N/A

**Phase of trial:** I

**Objectives:** The Primary Endpoint

An evaluation of the distribution of seed migrations to estimate the risk of markers migrating

- A clinically significant distance (10mm or greater)
- A clinically unsafe distance (40 mm or greater)

Marker (seed) location will be compared radiographically between the post-placement image and the pre-operative image. The position of the marker (seed) will be assessed in relation to anatomical landmarks and any change recorded in mm.

Secondary research questions include;

- Accuracy of initial placement – distance of the marker (seed) on radiographic imaging from the intended site of placement (e.g. lesion, marker clip, calcification);
- Percentage magnetic markers (seeds) within target area;
  - The target area will be detected by mammography on the day of surgery and is defined as within 10mm of the target lesion.
- Relationship between depth of marker (seed) and ease of transcutaneous detection;

- Marker (seed) depth to the nearest skin surface will be estimated sonographically
- Ease of detection measured by ability to detect the marker (seed) with Sentimag detector and the time to detect marker (seed) in seconds;

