#### Methods:

The marker (seed) will be inserted by trained and qualified healthcare professionals under image guidance (ultrasound or radiography) and removed with the surgical mastectomy (breast) specimen.

Sentimark will be placed in the lesion for which a patient is scheduled to have a mastectomy, a minimum of 2 days prior to surgery.

The depth of lesion and marker will be recorded by the radiologist

Confirmation of initial detectability with magnetometer immediately after placement and time to detection (seconds).

Assessment of distance of the magnetic marker (seed) from lesion on pre-operative mammography.

Check mammogram on morning of surgery to ensure Sentimark is still visible.

Surgeon checks that Sentimark can be detected transcutaneously during surgery.

Surgeon performs mastectomy

Record mastectomy weight. 25 patients (range of breast sizes (a minimum of three of each of small (<250g), and medium (250-500g), and five large (>500g) breasts).

Perform pathology assessment of mastectomy tissue and record any unexpected tissue reaction to the Sentimark device (minimum 10 patients)

All adverse events will be recorded from when the patient signs the informed consent until the final study visit.

25 patients

**Trial duration per participant:** 6 weeks maximum

**Estimated total trial duration:** Ten months

**Planned trial sites:** Single – University Hospital of South Manchester

**Total number of participants planned:** 25

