## Device

The device to be studied is a small (5mm x 0.9mm) metal magnetic marker (seed) that has soft magnetic properties. This means that when exposed to a magnetic field it becomes magnetic. The magnetism can then be detected using a magnetometer and probe which gives an audible and visual signal of the strength of response from the seed and as it is directional this can accurately guide the user to the site of the magnetic seed. The magnetometer is a CE approved device and is used worldwide for detecting iron oxide in sentinel lymph node biopsy procedures, and is proven in clinical practice. The seed itself will be deployed by a radiologist into the centre of the tumour site using a similar technique to that used to currently place a wire into the breast. The seed itself is cylindrical and in *in vivo* studies in goats have shown similar migration performance to that seen with radioactive seeds in human breast tissue.

The seed has also been tested in animal tissue models by UHSM radiologists and surgeons, and in these models it can be safely deployed by the radiologists using existing techniques. The device was detected and surgical resection was performed with 100% accuracy on all specimens. There is no radiation exposure from this device.

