#### 4.1.1 Primary and Secondary Endpoints/Outcome Measures

The Primary Endpoint:

An evaluation of the distribution of seed migrations to estimate the risk of markers migrating

- A clinically significant distance (10mm or greater);
- A clinically unsafe distance (40 mm or greater).

Marker (seed) location will be compared radiographically between the post-placement image and the pre-operative image. The position of the marker (seed) will be assessed in relation to anatomical landmarks and any change recorded in mm.

Secondary research questions include:

- Accuracy of initial placement – distance of the marker (seed) on radiographic imaging from the intended site of placement (e.g. lesion, marker clip, calcification);
- Percentage magnetic markers (seeds) within target area.
  - The target area will be detected by mammography on the day of surgery and is defined as within 10mm of the target lesion.
- Relationship between depth of marker (seed) and ease of transcutaneous detection;
  - Marker (seed) depth to the nearest skin surface will be estimated sonographically

- Ease of detection measured by ability to detect the marker (seed) with Sentimag detector and the time to detect marker (seed) in seconds

Other Endpoints:

- Safety and tolerability;
  - Tissue responses as assessed by gross pathology and histology will be described
  - Adverse Effects profile will be monitored
- Seed integrity post excision;
- Number of days the marker (seed) was in place;
- Mastectomy weight;
- Relationship between clinical characteristics and movement of the markers --  
If any markers migrate a clinically significant distance, a qualitative assessment will be carried out to see if there is a possible relationship between clinical characteristics seen in patients and movement of the marker. (e.g. Haematoma, placement of seed into fatty rather than soft tissue).

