## 4.2 Study Design

This is a single site, single arm, unblinded safety and feasibility cohort study investigating the use of magnetic marker seeds to localise breast tumours.

Expected duration of patient participation – Four to six weeks. This will equate to a 2-4 week period between invitation to join study and Study visit 2 when surgery occurs. And a 2-3 week period between surgery and the final follow-up Study visit 3.

Invitation – occurs immediately after surgical discussion on the patient’s surgical plan for removal of the breast cancer. Patient given an information leaflet about study.

- Follow-up phone call to patient more than 24 hours after invitation;
- Study visit 1 – Consultation with patient – consent taken for study. Eligibility confirmed and baseline data recorded. Placement of Sentimark device, mammogram taken to check placement, detectability of device confirmed, ultrasound performed to confirm depth of clip;
- Study visit 2 – day of surgery – check mammogram (this can occur on the day before surgery if the patients requires attendance for Sentinel Node

Biopsy as part of routine clinical care the day before surgery), check detectability of Sentimark seed, surgery performed;

- Study visit 3 – Routine follow-up appointment – Adverse effects recorded, oncological outcomes recorded and mastectomy weight.

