## 6. Trial Procedures

Assessments	Baseline Visit 1	Surgery Visit 2	Post surgery Visit 3 (2-3 wks post surgery)
Informed consent	X		
Medical history	X		
Pregnancy test (if pre menopausal)	X		
CRF/eCRF completion including data transfer and query resolution	X	X	X
Concomitant medication check	X	X	X
Review/reporting of patient AEs/SAEs		X	X
Place sentimark lesion and ultrasound	X		
Localise lesion during surgery		X	
Check detectability of seed with magnetometer	X	X	
Data collection in theatre		X	
Record migration of clip		X	
Mammogram	X	X	
Mastectomy specimen x-ray		X	

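### Ease of detection is recorded only as yes/no and seconds; the probe's graded signal should be recorded alongside them at the two checks already scheduled

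*Combined protocol and SAP*

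**What the plan says.** The secondary question is the "Relationship between depth of marker (seed) and ease of transcutaneous detection" (Section 4.1.1). Depth is specified: "Marker (seed) depth to the nearest skin surface will be estimated sonographically". Ease is specified in the same words in Sections 1, 4.1.1 and 7.2: "Ease of detection measured by ability to detect the marker (seed) with Sentimag detector and the time to detect marker (seed) in seconds".

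The timing of the checks comes from three places.

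- **Section 1, Methods.** At placement: "Confirmation of initial detectability with magnetometer immediately after placement and time to detection (seconds"). At operation: "Surgeon checks that Sentimark can be detected transcutaneously during surgery". Only the first of these mentions a time.
- **Section 4.2.** At Visit 1 the order is placement, mammogram, detectability, ultrasound for depth. Visit 2 has a mammogram and a further detectability check. The design is a "single site, single arm, unblinded safety and feasibility cohort study".
- **Section 6, schedule.** The row "Check detectability of seed with magnetometer" is ticked at Visits 1 and 2. No row covers signal strength or a reading before insertion. Ultrasound appears at Visit 1 only.

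The Device text in Section 3 says that the magnetometer and probe together give a graded output: the system "gives an audible and visual signal of the strength of response from the seed". No section asks for that output to be written down.

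Section 10.3 plans descriptive summaries, graphs and 95% confidence intervals, with a simple correlation between breast size and detectability. It names no method for depth. Section 4.1 lists mastectomy weight, lesion depth and ability to detect together as an exploratory aim.

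**The concern.** Section 3 (Potential Risks to Patients) names the failure that this endpoint should inform: a seed may lie too deep for the magnetometer to find it. The two chosen measures say least about that failure.

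- **Yes/no** is informative only if some seeds are missed. If all or nearly all are found, it cannot show where detection starts to weaken.
- **Seconds** vary among found seeds, but they mix signal with the operator's search technique. A seed that is not found has no time. The protocol gives no maximum search time and no rule for such a seed, so the deepest seeds could drop out of the very analysis meant to describe them.

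The graded output is produced at each check in any case. What is at stake is how much 25 patients can say about depth and breast size before the device is used in lumpectomy, the later use foreseen in Section 3 (Potential Benefits). The results also support the CE-mark application (Section 13).

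**Working it through.** **Inputs from the documents.** n = 25 (Section 10.1); 95% confidence level (Section 10.3). The documents give no power target, expected correlation, reliability or false-call rate for detection. Any such value below is an assumption.

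**1. The plan's only formal precision figure.** Sections 7.1 and 10.1 give 0 to 13% for 0 of 25 seeds migrating. The Wilson upper limit is z²/(n + z²) = 3.84/(25 + 3.84) = 13.3%, which agrees. The exact (Clopper-Pearson) limit is 1 − 0.025^(1/25) = 13.7%. The figure concerns migration and is not at issue.

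**2. Yes/no if every seed is found.** The mirror image for 25 of 25 detected is a lower 95% limit of 0.025^(1/25) = 86.3% (exact) or 25/28.84 = 86.7% (Wilson). The variance of the score is p(1 − p) = 1 × 0 = 0, so its correlation with depth or breast size is undefined.

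**3. Yes/no if one seed is missed.** With one miss in n, the correlation between missed and depth equals that seed's standardised depth divided by √(n − 1) = √24 = 4.90. The whole result is then one patient's depth.

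**4. Precision of any correlation at n = 25, with no measurement error.** The Fisher-z half-width is 1.96/√22 = 0.418. For an observed r = 0.5, atanh(0.5) = 0.549, so the limits are tanh(0.131) = 0.13 and tanh(0.967) = 0.75.

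**5. Effect of noise in the measure (illustration).** Observed r = true r × √reliability. Power to show a non-zero correlation = Φ(atanh(r) × √22 − 1.96). With an assumed true r of 0.5:

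| Assumed reliability | Expected observed r | 95% CI at that r | Power |
|---|---|---|---|
| 1.0 | 0.50 | 0.13 to 0.75 | 73% |
| 0.8 | 0.45 | 0.06 to 0.72 | 62% |
| 0.6 | 0.39 | −0.01 to 0.68 | 48% |
| 0.4 | 0.32 | −0.09 to 0.63 | 34% |

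The documents give a reliability for neither seconds nor signal. The table shows how noise acts, not how much one measure gains over the other.

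**6. Could a pre-insertion reading define detection?** Suppose a seed gives no usable signal. The blank and the later reading are then both noise, and the later one exceeds the blank with probability 1/2. If the later value is the maximum of k such readings, the probability is k/(k + 1), or 75% for k = 3. With an assumed true detection rate of 90%, this rule would report 0.90 + 0.10 × 0.5 = 95%, or 0.90 + 0.10 × 0.75 = 97.5%. A bare threshold at one blank would therefore create false detections.

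**The case against.** The strongest reply is that the question is about ease, and that whether a user finds the seed and how quickly measures ease directly. Signal strength answers a related physical question. Seconds are already continuous, so the plan does not rest on yes/no alone. The endpoint is secondary and descriptive, with no test or power target to fail. Section 10.3 promises to display and discuss sources of measurement error. The CRF is not among the documents, so it may already hold a signal field.

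Most of this stands. It is why signal should be added and should not replace seconds, and why the power column above is only an illustration. It does not answer the two gaps: yes/no without variation, and no time value for a seed not found. A general statement about measurement error does not supply a measurement that was never recorded.

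A reader might also infer that an unblinded operator with no blank reading will overstate detection. The documents do not support that.

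- The seed is visible on mammography and ultrasound (Section 1). There is imaging at Visit 1, a mammogram for Visit 2 and a specimen x-ray (Sections 4.2 and 6). A claimed location can be checked against these, although no formal comparison is scheduled.
- An operator can also miss a detectable seed, so error can run either way.
- A marker clip is named only as an example of an intended site. No section says that clips give a probe response.
- Recent iron oxide injection and chest-wall devices are excluded (Section 5.3).

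With true detection assumed at 90%, false-call rates of 10%, 25% and 50% among undetectable seeds would give 0.90 + 0.10 × f = 91%, 92.5% and 95%. Nothing in the documents fixes f.

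**Conclusion.** The point holds as a specific, inexpensive improvement. Ease of detection is recorded only as yes/no and seconds, although the device supplies a graded signal. If all 25 seeds are found, yes/no carries no information on depth or breast size. Seconds are affected by technique and undefined for a seed not found.

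These gaps follow from the definitions and need no assumption. The size of the loss does need one: at a true correlation of 0.5, reliabilities of 0.8 to 0.4 would reduce the observed value to 0.45 to 0.32. Even a noise-free measure would leave a wide interval at n = 25 (0.13 to 0.75).

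Two stronger conclusions should not be drawn. The documents do not show that detection rates will be inflated, and they do not show that signal is a better main outcome than time to find the seed.

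**What to change.** In Sections 1, 4.1.1 and 7.2, add the displayed Sentimag signal as a further measure of ease of detection, keeping yes/no and seconds.

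- **When.** At the Visit 1 and Visit 2 checks already in the Section 6 schedule.
- **Where.** At the skin point of strongest response or, if the seed is not found, over the site located on imaging. Each seed then has a value.
- **Analysis (Section 10.3).** Plot signal against ultrasound depth and against mastectomy weight, and report each correlation with its 95% confidence interval. Depth is measured at Visit 1 only, so state that the Visit 2 analysis uses Visit 1 depth.
- **Optional.** Record a brief probe reading over the same skin point before insertion, as descriptive background only. Do not redefine detection as any signal above that single reading (step 6 of the working).

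The cost is one CRF number per check, plus a few seconds if the optional reading is taken, with equipment already in use and no extra visit. The change assumes that the display can be read as a number or graded level, which the sponsor should confirm. It leaves the operator unblinded, and the signal will still depend partly on how the probe is handled. The gain in precision cannot be derived from the documents.

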#### Other End-points

- Safety and tolerability
  - Tissue responses as assessed by gross pathology and histology will be described
  - Adverse Effects profile will be monitored
- Seed integrity post excision;
- Number of days the marker (seed) was in place;
- Mastectomy weight
- Relationship between clinical characteristics and movement of the markers -- If any markers migrate a clinically significant distance, a qualitative assessment will be carried out to see if there is a possible relationship between clinical characteristics seen in patients and movement of the marker. (e.g. Haematoma, placement of seed into fatty rather than soft tissue)

**Type of trial:** Single site, single arm, open label safety and feasibility cohort study of using magnetic marker seeds to localise breast tumours.

**Trial design and methods:** The magnetic marker system (Sentimark® Magnetic Marker System) is a sterile, single use device composed of a magnetic marker (seed) preloaded in a delivery system. The magnetic seed is approximately 5mm long and 0.9mm in diameter.

The seed is intended to be temporarily placed within the breast and removed within 28 days. The seed, when used in conjunction with the Sentimag® System (base unit and probe), can be used as a guide for the surgeon to facilitate excision of tissue. The Tissue

Marker (seed) is visible using ultrasound and mammography.

The study is a first-in-human study using this particular magnetic seed and designed to test the feasibility and safety of using the marker (seed) in breast cancer patients. The data will support the application for a CE mark.

The study will be carried out in patients requiring a mastectomy. In this population, the full cycle of marker (seed) deployment and removal can be evaluated, but as the breast is being removed as part of the planned cancer treatment, patient treatment will be unaffected should the magnetic seed not perform as intended.

#### Methods:

The marker (seed) will be inserted by trained and qualified healthcare professionals under image guidance (ultrasound or radiography) and removed with the surgical mastectomy (breast) specimen.

Sentimark will be placed in the lesion for which a patient is scheduled to have a mastectomy, a minimum of 2 days prior to surgery.

The depth of lesion and marker will be recorded by the radiologist

Confirmation of initial detectability with magnetometer immediately after placement and time to detection (seconds).

Assessment of distance of the magnetic marker (seed) from lesion on pre-operative mammography.

Check mammogram on morning of surgery to ensure Sentimark is still visible.

Surgeon checks that Sentimark can be detected transcutaneously during surgery.

Surgeon performs mastectomy

Record mastectomy weight. 25 patients (range of breast sizes (a minimum of three of each of small (<250g), and medium (250-500g), and five large (>500g) breasts).

Perform pathology assessment of mastectomy tissue and record any unexpected tissue reaction to the Sentimark device (minimum 10 patients)

All adverse events will be recorded from when the patient signs the informed consent until the final study visit.

25 patients

**Trial duration per participant:** 6 weeks maximum

**Estimated total trial duration:** Ten months

**Planned trial sites:** Single – University Hospital of South Manchester

**Total number of participants planned:** 25

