## Potential Risks to Patients

The device itself is a small piece of metal and in itself does not offer a likely safety risk.

- Migration of the seed – the seed is cylindrical and therefore once placed in the breast it has the potential to migrate along the path of the needle that was used to deploy it. When deployed into mammary soft tissue in animal models the device has not migrated. This study will involve placing the device in women having mastectomy so even if the device migrates it will not affect patient's cancer care (as the whole breast will be removed along with the device no matter where it is located in the breast).
- Failure to detect the seed – the seed is small and the magnetic field generated is proportional to the size of the seed. This study aims to assess whether the seed can be detected in all sizes of breast as in some cases it

may be possible that the seed lies too deep in the breast to be detected using the magnetometer. To ensure safe resection of the cancer, each patient in this study will be under-going a planned mastectomy, to ensure that the device is fully removed even if detection should fail.

- Tissue acceptance – the seed is produced from a single material and has demonstrated biocompatibility through ISO-10993 biocompatibility evaluation including demonstration of tissue acceptance in mammary tissue of goats (28-day implantation period). Bone wax is used as a terminal plug for Sentimark device. Bone wax is commonly used for the same purpose in brachytherapy and RSL needles. Some reaction to bone wax may occur, such as an allergic reaction or foreign body reactions (e.g. granulomas), as bone wax is a minimally resorbable implantable substance.

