## **5.6 Withdrawal of Subjects**

Safety of the study participants will be monitored by the Chief Investigator. It is unlikely there will be Serious Adverse Events directly related to the Sentimark as it is similar to devices currently in use to mark breast cancer location. The study involves an intervention of Sentimark placement within the breast. Patients may withdraw consent to have this procedure performed in which case this will be recorded and the patient will be withdrawn from the study and will be replaced by another subject. If a patient withdraws consent to the study once the Sentimark has been placed, they will be withdrawn from the study but information on the cancer

excision surgery will be recorded to ensure the Sentimark magnetic marker (seed) was removed as part of the breast cancer surgery.

Each participant has the right to withdraw study at any time. In addition, the investigator may discontinue a participant from the study at any time if the investigator considers it necessary for any reason including:

- Ineligibility (either arising during the study or retrospective having been overlooked at screening);
- Significant protocol deviation;
- Significant non-compliance with treatment regimen or study requirements;
- An adverse event which requires discontinuation of the study medication or results in inability to continue to comply with study procedures;
- Disease progression which requires discontinuation of the study medication or results in inability to continue to comply with study procedures;
- Consent withdrawn;
- Lost to follow up.

It is understood by all concerned that an excessive rate of withdrawals can render the study un-interpretable; therefore, unnecessary withdrawal of patients should be avoided. Should a patient decide to withdraw from the study, all efforts will be made to report the reason for withdrawal as thoroughly as possible.

Withdrawal from the study will result in exclusion of the data for that participant from analysis.

The reason for withdrawal will be recorded in the CRF.

If the participant is withdrawn due to an adverse event, the investigator will arrange for follow-up visits or telephone calls until the adverse event has resolved or stabilised.

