## 7. Assessment of Efficacy

### 7.1 Primary Efficacy Parameters

#### The Primary Endpoint:

An evaluation of the distribution of seed migrations to estimate the risk of markers migrating

- A clinically significant distance (10mm or greater);
- A clinically unsafe distance (40 mm or greater).

Marker (seed) location will be compared radiographically between the post-placement image and the pre-operative image. The position of the marker (seed) will be assessed in relation to anatomical landmarks and any change recorded in mm.

Formally the 95% CI if 0 out of 25 seeds migrate >10mm is 0-13%. However, findings will be considered in conjunction with other observations:

- The observed distribution of migration (e.g. how variable is this distribution and how close does it lie to the limits)
- For any seeds migrating >10mm, a qualitative assessment of underlying characteristics such as haematoma or placement into fatty tissue (both reported as causes of migration in RSL procedures)
- Abnormal tissue responses will be assessed by gross pathology and histology, as part of the safety endpoint.

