### 9.2.3 Reporting Form

The reporting form template for the summary SAE tabulation is given in the Appendix of this document.

The table gives a cumulative overview of the reportable events per clinical investigation and will be updated and transmitted to participating NCAs each time a new reportable event or a new finding to an already reported event is to be reported. More detailed information has to be provided on request of an NCA, if so requested by using the individual reporting form. The sponsor shall identify the new/updated information in the status column of the tabular form featured in the Appendix as:

a = added = new reportable event;

m = modified = new finding/update to an already reported event;

u = unchanged.

Changes in a line should be highlighted in bold and/or colour in the respective column.

The reporting form is study specific and covers only a given clinical investigation, defined by a distinct clinical investigation plan. English is the recommended language for the reporting form. The report should be sent by email in Excel to the participating NCAs, or an equivalent format which allows using the inserted filters. The reporting to MHRA shall use the form template for the summary SAE tabulation as given in the Appendix of MEDDEV 2.7.3 December 2010.

Safety Oversight:

The Trial Steering Committee will meet once all patients have completed the study or earlier if considered necessary by the Chief Investigator. They will consider all Serious adverse events and adverse events and the main safety and efficacy outcomes. Notably they will discuss:

Morbidity and safety of seed placement – recording of any morbidity as a result of Study visit 1 or 2;

Detectability of the seed in the breast. – measured at Study visits 1 and 2 using the hand-held magnetometer;

Assessment of migration of the seed from time of deployment to time of surgery.

Measured on difference in position of magnetic marker (seed) from the cancer

between Study Visits 1 and 2, and assessed on mammograms by a Consultant Radiologist.

If any markers migrate a clinically significant distance, a qualitative assessment will be carried out to see if there is a possible relationship between clinical characteristics seen in patients and movement of the marker. (e.g. Haematoma, placement of seed into fatty rather than soft tissue)

Adverse tissue responses as assessed by gross pathology and histopathology.

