### **10. Statistics**

#### **10.1 Sample Size**

This protocol has been developed with [name] Medical Statistician at Manchester University.

The sample size has been set at 25 patients to achieve a balance between having sufficient numbers to observe any unexpected patterns of seed migration and keeping to a minimum the number of patients exposed to any risk through participating in the study as no direct benefit is to be expected for participants who consent to taking part in the trial.

RSL seeds are a product similar in size and shape to Sentimark, in widespread clinical use in the same indication, and considered to be safe and effective. In the literature Alderliestenxiii, et al. [2011] report a mean migration of 0.8mm, range 0 to 2.8mm (N=10) for RSL seeds which was considered “clinically negligible” by the authors.

Migration of Sentimark in preclinical studies where the seed is deployed in soft mammary tissue showed a mean migration of 0.95mm, range 0 to 3.6mm (N=10) and no abnormal tissue reaction. Migration observed is substantially similar to that reported by Alderliesten et al for RSL seeds.

From the experience with RSLs, clinically significant migration of radioseeds (greater than 1cm) in larger studies has been reported in 3/456 placements (Grayxiv et al [2004], Sungxv et al [2013]). However when it does occur the reason is often either a pre-existing or newly formed haematoma or placement of the seed into fatty rather than soft tissue.

For this reason, clinical characteristics of patients in whom a seed migrates more than 1cm will be carefully evaluated.

Formally, the 95% CI if 0 out of 25 seeds migrate >10mm is 0-13%. However, findings will be considered in conjunction with other observations including:

- The observed distribution of migration (e.g. how variable is this distribution and how close does it lie to the limits)
- For any seeds migrating >10mm, a qualitative assessment of underlying characteristics such as haematoma or placement into fatty tissue (both reported as causes of migration in RSL procedures)
- Abnormal tissue responses will be assessed by gross pathology and histology, as part of the safety endpoint.

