## **10.3 Analysis**

Simple descriptive summary statistics of the main parameters will be derived together with a graphical presentation of the raw data. Percentages for categorical variables, means, standard deviations, medians and range values for quantitative factors will be calculated as appropriate. 95% confidence intervals will also be presented to provide a measure of accuracy for the estimates.

The relationship between breast size and detectability of the seed by the magnetometer will be assessed using simple correlational analysis.

The statistical software package, SPSS version 22, will be used for the statistical analysis.

Sources of measurement error will be graphically displayed, reviewed and discussed as appropriate.

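### Tissue response is part of the safety endpoint with no subset stated, but the Summary is satisfied by any 10 of the 25 specimens

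*Combined protocol and SAP*

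**What the plan says.** Section 4.1.1 lists tissue response under safety and tolerability, among the other endpoints: "Tissue responses as assessed by gross pathology and histology will be described". The Summary's endpoint list says the same. Sections 7.1 and 10.1 bring it into the interpretation of the migration result: "Abnormal tissue responses will be assessed by gross pathology and histology, as part of the safety endpoint". Under Safety Oversight in section 9.2.3, the Trial Steering Committee is to discuss "Adverse tissue responses as assessed by gross pathology and histopathology". None of these places limits the assessment to some of the patients.

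The Methods part of the Summary does. There the instruction is to assess the mastectomy tissue and "record any unexpected tissue reaction to the Sentimark device (minimum 10 patients". The same list sets minimum numbers by breast size, but no rule for choosing the specimens that go to tissue assessment.

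Two other provisions bear on the denominator. Section 10.3 says that "95% confidence intervals will also be presented to provide a measure of accuracy for the estimates". Section 5.6 says that "Withdrawal from the study will result in exclusion of the data for that participant from analysis", and it lists adverse events among the reasons for which an investigator may discontinue a participant.

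**The concern.** The study is first-in-human for this seed and its data are meant to support a CE mark (Summary; section 13). Section 3 already names a plausible local effect: "Some reaction to bone wax may occur, such as an allergic reaction or foreign body reactions (e.g. granulomas". Histology of the seed site is the direct way to look for it.

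As written, a site complies by assessing ten specimens of its own choosing. Two things follow. First, a finding of no reactions would be much less informative than the cohort size suggests. Second, nothing prevents the ten from being unrepresentative. For example, the Summary allows placement as little as 2 days before surgery and intends removal within 28 days, so ten convenient specimens could lean towards short placements.

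The recording is also loose. The thing to be recorded is a tissue response in section 4.1.1, an unexpected reaction in the Summary, an abnormal one in sections 7.1 and 10.1, and an adverse one in section 9.2.3. A granuloma, having been named in advance as possible, might or might not count as unexpected. If a routine pathology report does not mention the seed site, the documents do not say whether that means no reaction or no assessment.

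**Working it through.** **Inputs.** Planned patients: 25 (section 10.1). Floor for tissue assessment: 10 (Summary, Methods). Confidence level: 95% (sections 10.1 and 10.3). The documents give no expected tissue-reaction rate, so any rate used below is an assumption.

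**Step 1: reproduce the plan's own figure.** Sections 7.1 and 10.1 give 0–13% for 0 of 25 seeds migrating. For 0 events in n:

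- Wilson upper limit = z²/(n + z²), with z = 1.96. At n = 25: 3.84/28.84 = 13.3%, which matches the stated 13%.
- Exact (Clopper-Pearson) upper limit = 1 − 0.025^(1/n). At n = 25: 13.7%.

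The plan's figure concerns migration, but the same formulas apply to any event not seen in n patients.

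**Step 2: apply them to tissue response with no reactions seen.**

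| Specimens assessed | Exact upper limit | Wilson upper limit |
|---|---|---|
| 25 | 13.7% | 13.3% |
| 15 | 21.8% | 20.4% |
| 10 | 30.8% | 27.8% |

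The limit at the floor is 2.1 (Wilson) to 2.2 (exact) times the limit with all 25 assessed.

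**Step 3: chance of seeing at least one reaction,** 1 − (1 − p)^n, for assumed true rates p.

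| Assumed rate | n = 25 | n = 10 |
|---|---|---|
| 5% | 72% | 40% |
| 10% | 93% | 65% |
| 20% | 99.6% | 89% |

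**Step 4: effect of the exclusion rule in section 5.6.** Suppose 1, 2 or 3 of 25 participants are withdrawn after placement and not replaced (an assumption). With no reactions among the rest, the exact limit becomes 14.2%, 14.8% or 15.4% (Wilson 13.8%, 14.3%, 14.9%). In precision this is small beside the effect of the floor. The more serious problem is which data are lost: read literally, a participant withdrawn because of an adverse event leaves the analysis, and that is the participant most likely to be informative about safety.

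**The case against.** The strongest reply is that a minimum of 10 is a floor. The site may intend to assess all 25, and nothing in the text forbids it. That stands: a reader might infer that the plan contradicts itself, or that only ten specimens will be examined, and the documents support neither. Ten is the least the text allows, not the number expected.

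Second, tissue response is one of the other endpoints and is to be described. The plan sets no target rate or interval for it, and section 10.3 applies percentages and intervals to the main parameters as appropriate. This also stands, and it limits the point to precision and selection. A description still needs a stated number of patients behind it.

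Third, adverse events are recorded for every patient from consent (Summary, Methods), serious ones are reportable (section 9.1), and the committee considers all of them (section 9.2.3). So the gap from the floor is confined to histological reactions not classed as adverse events. For the same reason, exclusion under section 5.6 removes data from analysis, not from safety reporting.

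Fourth, the Summary does tie the recording to the device, the schedule in section 6 includes a specimen x-ray that could help to locate the seed, and the CRF is not among the documents. It therefore cannot be said that the CRF lacks a seed-site item, only that the protocol does not define one.

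Two further inferences should be resisted. A reader might say that the effect of withdrawal is undefined. It is defined: section 5.6 excludes the data and replaces a patient who withdraws before placement. The difficulty is what that rule does to safety data. A reader might also say that 0 of 10 in patients merely repeats the preclinical result. In section 10.1 the N=10 is attached to the migration figures, and the number of tissue assessments behind the absence of an abnormal reaction is not given.

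**Conclusion.** The point holds as an inconsistency between the Summary's floor and the unrestricted wording elsewhere. Compliance with the floor alone would leave a 95% upper limit of 30.8% exact (27.8% Wilson) after no reactions, against 13.7% (13.3%) with all 25, and would leave the choice of specimens open. The withdrawal rule is a smaller matter numerically, but as worded it can remove a participant withdrawn for an adverse event from the analysis.

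The figures assume that no reactions are seen, that patients are independent, and that 25 seeds are placed and 25 specimens obtained. No stated target is breached and the primary migration endpoint is unaffected. Severity: minor to moderate.

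**What to change.** 1. In the Methods part of the Summary, replace the bracketed floor of ten with all patients in whom a seed was placed and a mastectomy specimen obtained. State the same population in section 4.1.1.
2. Record reaction at the seed site as present, absent or not assessed. Count silence in a routine pathology report as not assessed.
3. In section 10.3, report seeds placed, specimens examined and seed sites assessed, with reasons for any not assessed. Use sites assessed as the denominator for the percentage and its 95% confidence interval.
4. In section 5.6, limit the exclusion of a withdrawn participant's data so that tissue-response and other safety data already gathered after placement stay in the safety summary, subject to the consent given.

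**Cost.** Seed-site reporting on up to 15 more specimens (25 − 10). Every specimen is already removed and scheduled for x-ray (section 6), post-operative histology is already recorded (section 5.7), and seed integrity after excision is already an endpoint (section 4.1.1). The documents do not give the extra pathology time per specimen. Beyond that, the change needs one recording item, short edits to the Summary and sections 4.1.1, 5.6 and 10.3, and one amendment submitted to the ethics committee and regulatory authorities (section 13).
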